7.2.3 Other Assessments

Neuropsychiatric Inventory (NPI): The NPI is a well-validated, reliable, multi-item instrument to assess psychopathology in AD based on an interview with the caregiver (Cummings et al, 1994). The interview is also relatively brief (15 minutes). It evaluates both the frequency and severity of 12 behavioral areas including delusions, hallucinations, dysphoria (depression) anxiety, agitation/aggression, euphoria, disinhibition, irritability, lability, apathy, aberrant motor behavior, appetite and eating changes and night-time behaviors.

Frequency assessments range from 1 (occasionally, less than once per week) to 4 (very frequently, once or more per day or continuously) as well as severity (1= mild, 2 = moderate, 3 = severe). Distress is rated by the study partner or caregiver and ranges from 0 (no distress) to 5 (very severe or extreme). The overall score and the score for each subscale are the product of severity and frequency. Scores range from 0-144 with higher scores indicating a greater

presence of neuropsychiatric symptoms. The NPI will be administered at Baseline (Month 18 of TTP488-301), and at Months 6, 12, 18, and 24 or in the event of early termination.

Resource Utilization in Dementia (RUD Lite): The RUD Lite is a validated and reliable questionnaire which assesses the health care resource utilization (HCRU) of the patient and caregiver and measures the level of formal and informal care (Wimo et al, 2012). The RUD Lite consists of items about caregiver time, caregiver work status, caregiver HCRU (e.g., hospitalization, ER visits, health care professional visits and medication), patient living accommodation, and patient HCRU. It takes approximately 15-20 minutes to complete and is usually interview administered by any health care professional. This scale will be administered at Baseline (Month 18 of TTP488-301) and at Months 6, 12, 18, and 24 or in the event of early termination.

Dementia Quality of Life (DEMQOL) –Proxy: The DEMQOL-Proxy questionnaire is a validated and reliable questionnaire that is interview administered and completed by the caregiver about the patient’s health related quality of life (Smith et al, 2005). It consists of 31 items representing 5 domains (daily activities and looking after yourself, health and well-being, cognitive functioning, social relationships, and self-concept) and takes approximately 20 minutes to complete. Higher scores indicate better health related quality of life. This scale will be administered at Baseline (Month 18 of TTP488-301) and at Months 6, 12, 18, and 24 or in the event of early termination.

7.3 SUICIDALITY ASSESSMENTS

The Columbia Suicide Severity rating Scale (C-SSRS) is a joint interview with the caregiver and patient that systemically assesses suicidal ideation and suicidal behavior (Posner et al, 2011). This scale will be administered at Screening Visit to evaluate life time suicide attempt, suicide behaviors, and other non-suicidal self-injuries. Positive responses on the C-SSRS will be mapped to the Columbia Classification Algorithm of Suicide Assessment (C-CASA) for classification and reporting using a standard algorithm.

The C-SSRS will be used to assess suicide ideation or behavior at each study visit. If there are “yes” answers on items 4, 5 or on any behavioral question of the C-SSRS, a professional suicide risk assessment should be done as soon as possible to determine whether it is safe for the subject to continue participation in the trial. A risk assessment will be done by a qualified mental health professional with expertise in the evaluation of suicidality in the elderly (e.g., psychiatrist,

geriatrician or neurologist specializing in treatment of patients with AD) to determine whether it is safe for the subject to participate in the study. A change from baseline to a yes on any of these items will also constitute an AE and will be documented as such.

7.4 PLASMA FOR ANALYSIS OF AZELIRAGON AND METABOLITE CONCENTRATIONS

Blood samples for pharmacokinetic analysis will be collected at Baseline (Month 18 of TTP488-301), Months 6, 12, 18 and 24 or at Early Termination.

Blood samples (4 mL) to provide plasma for pharmacokinetic analysis will be collected into appropriately labeled tubes containing dipotassium (K2) EDTA at times specified above.

Following blood collection, the tubes will be placed in an ice-water bath (maximum 60 minutes) until centrifugation. Samples will be centrifuged at approximately 1700 g for about 10 minutes at 4°C. The plasma will be stored in appropriately labeled screw-capped polypropylene tubes at approximately -20°C within 1 hour of collection.

For azeliragon metabolites, samples may be analyzed at the Sponsor's discretion.

Samples will be analyzed using a validated analytical method.

The shipment address and assay lab's contact information will be provided to the investigator site prior to initiation of the trial.

7.5 PLASMA FOR ANALYSIS OF TOTAL A β , A β (1-40), A β (1-42)

Blood samples for plasma biomarkers analysis will be collected prior to dosing on Baseline (Month 18 of TTP488-301), Months 6, 12, 18, and 24 or at Early Termination.

Blood samples for plasma biomarkers (6 mL for A β analysis) will be collected into appropriately labeled tubes containing dipotassium (K2) EDTA at times specified above.

Samples will be centrifuged at approximately 1700 g for about 10 minutes at 4°C. The plasma will be stored in appropriately labeled screw-capped polypropylene tubes at approximately -

70°C within 1 hour of collection. Instructions on collection, processing, storage and shipment of the sample will be provided in a separate laboratory manual.

7.6 BLOOD VOLUME

Total blood sampling volume for the individual participants is approximately 106 mL.

Sample Type	Sample Volume (mL)	Number of Sampling Times	Total Volume (mL)
Routine Laboratory	16.5	4	66
PK	4	4	16
Biomarkers (A β)	6	4	24
TOTAL (mL)			106

8.0 ADVERSE EVENT REPORTING

8.1 ADVERSE EVENTS

An adverse event (AE) is any untoward medical occurrence in a clinical study participant administered a pharmaceutical product. Study drug treatment does not necessarily have a causal relationship with the AE. An AE, therefore, can be any unfavorable change in structure, function or chemistry (including abnormal clinical lab results, or ECG findings), symptoms, signs, or diseases temporally associated with the use of a medicinal (investigational) product, whether or not related to the medicinal (investigational) product, as defined by ICH.

The criteria for determining whether an abnormal objective test finding should be reported as an adverse event are as follows:

- Test result is associated with accompanying symptoms, and/or
- Test result requires additional diagnostic testing or medical/surgical intervention, and/or
- Test result leads to a change in study dosing or discontinuation from the study, significant additional concomitant drug treatment, or other therapy, and/or
- Test result is considered to be an adverse event by the investigator or sponsor.

Repeating an abnormal test, in the absence of any of the above conditions, does not constitute an adverse event. Any abnormal test result that is determined to be an error does not require reporting as an adverse event.

8.2 REPORTING PERIOD

Adverse event reporting will commence as soon as the study participant has been dosed, unless the event is deemed to be related to study procedures. The study-related procedure might include discontinuation from or decrease in current therapy, a study-specific assessment or scale, or a study-specific procedure. Events associated with such study-specific procedures prior to initial administration of study drug will be tracked as AEs from the time when the study participant signed the ICF.

SAE reporting will commence from the time the participant provides informed consent through last subject visit at Month 24. Any SAE occurring after the reporting period must be promptly reported if a causal relationship to study treatment is suspected.

All events, including pre-existing conditions that are not associated with study-specific procedures, which worsen after the study participant has signed the ICF, but occur prior to initial administration of study drug, are not considered AEs and will be captured under medical history. However, worsening of such conditions after initial administration of study drug will be designated as AEs.

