Upon completion of the study and locking the database, protocol-planned analysis of ADAS-cog data from 100% of subjects who were ongoing or who had completed 18 months at the time of study termination were performed. Analysis showed a beneficial effect of less cognitive decline in the 5 mg/day group compared to placebo at Month 18 (delta = 3.1, $p = 0.008$, analysis of covariance [ANCOVA] with multiple imputation). To confirm robustness of effect to statistical analysis procedures, this difference was found to be significant using other statistical models (ANCOVA with last observation carried forward [LOCF; $p = 0.03$] and generalized estimating equations [GEE; $p = 0.03$]).

Analysis was done to examine the impact of off-treatment data on analysis conclusions. Statistical analysis on ADAS-cog was performed using all available on-treatment data (“on

treatment” defined as data collected within 45 days of the last dose of study medication). Forty-five days was selected based on the long half-life of azeliragon (mean = 18 days in elderly participants) and the demonstration of measureable, appreciable concentrations during that time frame following the last dose. Mean changes in ADAS-cog show numerical active-placebo differences favoring the 5 mg/day dose group over time at all time points, with nominal significance at Month 18 (delta=2.7, p = 0.03).

The key secondary measure of CDR-sb at 18 months showed a numerical difference favoring 5 mg azeliragon over placebo CDR-sb (LOCF, delta = 0.73, p = 0.1)

The TTP488-301 Phase 3 study is enrolling patients with mild Alzheimer’s disease. Subgroup analyses of data in Study TTP488-203 based on baseline severity of AD (mild or moderate), planned in the protocol and SAP, showed a more pronounced benefit of treatment with azeliragon among subjects with mild disease (MMSE 21 or more). In patients with mild AD, the difference in ADAS-cog mean change from baseline at 18 months was 4.0 (p = 0.018). In addition, a nominally statistically significant difference in CDR-sb mean change from baseline was demonstrated (delta = 1, p = 0.02) when comparing azeliragon 5 mg + SoC with placebo + SoC at Month 18. Thus, in the Phase 2 trial statistically significant differences between azeliragon 5 mg/day and placebo on cognition and global performance (using USA FDA agreed upon Phase 3 registration measures of ADAS-cog and CDR-sb) have been demonstrated.

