5.2 BREAKING THE BLIND

TTP488-303 is an open label study.

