1.5 Study Design

This is an open-label extension study in patients with mild Alzheimer's disease who have successfully completed participation in the azeliragon Phase 3 TTP488-301 (STEADFAST) trial. Patients may receive azeliragon 5 mg/day for up to 2 years.

Participants were required to continue to be on SoC of a stable background acetylcholinesterase inhibitor therapy and / or memantine and continue the therapy for the duration of the trial, unless the investigator judges that the dose needs to be reduced or stopped due to a safety and/or tolerability reason.

Subjects were expected to participate in approximately 9 outpatient visits including baseline which is the same visit at the Month 18 visit in the TTP488-301 study.

Protocol TTP488-301 included two studies with a common infrastructure (A-study and B-study). Participants from either study are allowed to roll over into this open-label extension study.

A-study is conducted at multiple sites in the US and Canada. B-study is conducted at multiple sites in the US, Canada, Ireland, UK, South Africa, New Zealand, and Australia.

This study was terminated prematurely before participation outside of the US and Canada began; therefore, this study is conducted at multiple sites in the US and Canada.

The overall structure of the study includes the following periods:

Baseline Study Period: (Month 18 visit of TTP488-301): At the Month 18 visit of TTP488-301, subjects who met eligibility requirements were offered enrollment into this open-label extension study. Subjects had baseline assessments for efficacy and safety measures, including PK assessments.

Treatment Period: (Day 1 (Month 18 visit of TTP488-301) — Month 24): Subjects were treated with open-label azeliragon 5 mg QD. Efficacy and safety measures were taken. Blood samples were taken and subjects have assessments for safety and PK.

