4.2.1 Treatment-emergent Adverse Events

Adverse events will be coded using Medical Dictionary for Regulatory Activities (MedDRA) Version 16.0 or above. Adverse event coding will be done to the lowest level term (LLT). Adverse events will be summarized by System Organ Class (SOC) and preferred terms (PT).

Definitions:

- A treatment-emergent adverse event (TEAE) is an event that is observed or reported after administration of study medication that was not present prior to study medication administration or an event that represents the exacerbation of a pre-existing event.

- An adverse withdrawal is a subject who withdrew from the study due to an adverse event.
- A serious adverse event (SAE) is an AE that is classified as serious according to the criteria specified in the study protocol.

Safety and tolerability variables based on adverse events include the following:

- Proportions of subjects with TEAEs by Preferred Term and decreasing frequency of AEs
- Proportions of subjects with TEAEs by System Organ Class and Preferred Term
- Proportions of subjects with related TEAEs
- Proportions of subjects with severe TEAEs
- Proportions of subjects with treatment-emergent SAEs.
- Subjects with TEAEs that result in study termination.

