6.2 Missing Data

In general, missing clinical data will not be imputed, except where explicitly defined. In the event of study withdrawal, a subject's final assessment will be used as the endpoint value, if applicable. For Trail Making Test A & B, if the assessment was not done due to cognitive reasons, the max score would be imputed. Note that the reason for "not-done" assessment is captured in the eCRF, and the specify field provides reason why. If the reason relates to cognitive reasons, the maximum time for Trails A (150 seconds) or for Trails B (300 seconds) is used.

Data are considered to be "on-treatment" if the assessment or collection follows the first administration of study medication and if the assessment occurs within 45 days following the final administration of study medication, justified based on the long half-life of this drug.

Dates with missing fields will not have days imputed.

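### Unconditional SAE reporting ends at the Month 24 visit, with no stated end for early terminators, while the SAP counts 45 further days as on-treatment

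*Protocol*

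**What the plan says.** **Reporting period.** Protocol 8.2 states: "SAE reporting will commence from the time the participant provides informed consent through last subject visit at Month 24". After that a condition applies: "Any SAE occurring after the reporting period must be promptly reported if a causal relationship to study treatment is suspected". The section gives no end of SAE reporting for subjects who leave through the Early Termination visit (Protocol 6.2). SAP 1.5 records that "This study was terminated prematurely before participation outside of the US and Canada began", so that route is not a side case.

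**Last dose and last contact.** Dosing is daily throughout the treatment period (Protocol 5.3.2). Month 24 is the last scheduled visit and carries the end-of-study procedures (Table 1; Protocol 6.1.9). No later safety contact is planned.

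**On-treatment window.** Under SAP 6.2, data count as on-treatment if they follow the first dose and "if the assessment occurs within 45 days following the final administration of study medication, justified based on the long half-life of this drug". Protocol 1.1.3 gives the origin of the figure: "Forty-five days was selected based on the long half-life of azeliragon (mean = 18 days in elderly participants".

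**TEAE definition.** In SAP 4.2.1 a TEAE "is an event that is observed or reported after administration of study medication that was not present prior to study medication administration", or is the worsening of an existing event. It has no end date and does not refer to the 45 days.

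**Causality.** Relationship to study drug is the investigator's judgment (Protocol 8.4), and "TTP488-303 is an open label study". Three provisions widen capture after the last visit:
- Protocol 8.4 handles events of unknown causality as related for reporting.
- Protocol 8.7.1 requires notification, at any time after the study, of a malignancy in a participant or a congenital anomaly in offspring, whatever the cause.
- Protocol 8.7 follows AEs already ongoing: those judged not related to resolution or for 60 days, those judged related to resolution or loss to follow-up.

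**The concern.** Safety is the primary endpoint. For a completer, unconditional SAE reporting closes at about the time of the last dose, yet the SAP treats the next 45 days as still on drug. Within those days, whether a new SAE reaches the database depends mainly on one person's opinion of its cause, formed with full knowledge of treatment. In this population a fall, an episode of confusion or a death can readily be put down to the underlying disease and left unreported.

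The open-ended TEAE definition turns this into an analysis problem. A post-visit SAE attributed to the drug is reported and counts as treatment-emergent. The same event attributed to the disease is never collected. The late part of the SAE table is thus selected by attribution, and a reader of the table cannot see it.

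The documents allow for exposure after the last dose elsewhere. The 18-month Phase 2 study had a safety follow-up visit at 21 months (Protocol 1.1.3), and the contraception and pregnancy-notification rules run for 90 days after the last dose (Protocol 4.3.1). Routine SAE collection has no such extension.

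For early terminators the position is less clear still, since Protocol 8.2 ties the end of reporting to a visit they do not attend.

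**Working it through.** The plan gives no figure of its own to reproduce. The check compares the texts and then sizes the window.

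**1. What happens to a new SAE with onset after the last visit but within 45 days of the last dose**

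| Type of event | Reportable? | Source |
|---|---|---|
| Drug suspected | Yes, no time limit | Protocol 8.2 |
| Causality unknown to the investigator | Yes, handled as related | Protocol 8.4 |
| Malignancy in the participant, or congenital anomaly in offspring | Yes, if the site learns of it | Protocol 8.7.1 |
| AE already ongoing at the last visit and judged not related | Followed to resolution or 60 days | Protocol 8.7 |
| Any other new SAE judged not related | No routine route | none |

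The last row is the gap.

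**2. Drug remaining.** Input: mean half-life 18 days (Protocol 1.1.3), assuming first-order decline. Fraction remaining at day t = 0.5^(t/18).
- Day 14: 0.5^(14/18) = 58%
- Day 30: 0.5^(30/18) = 31.5%
- Day 45: 0.5^(45/18) = 0.5^2.5 = 17.7%

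**3. Share of on-treatment time.** Inputs: dosing duration T on the scheduled study days (Table 1) and the 45-day window (SAP 6.2). Share = 45/(T + 45).

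| Last dose at | T (days) | Share |
|---|---|---|
| Month 6 | 180 | 45/225 = 20.0% |
| Month 12 | 360 | 45/405 = 11.1% |
| Month 18 | 540 | 45/585 = 7.7% |
| Month 24 | 720 | 45/765 = 5.9% |

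The first three rows are upper bounds. They assume that unconditional reporting stops on the day of the last dose, which Protocol 8.2 does not say for early terminators. If it stops at an Early Termination visit v days after the last dose, the share is (45 − v)/(T + 45). As an illustration, with v = 14 the Month 6 figure becomes 31/225 = 13.8%.

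**4. Events in the window.** The documents give no SAE rate. Assuming a range of 5 to 30 SAEs per 100 patient-years, the expected number per 100 subjects is rate × 45/365.25:
- 5 per 100 patient-years: 0.6
- 10: 1.2
- 20: 2.5
- 30: 3.7

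These counts include SAEs that remain reportable under step 1, so at each assumed rate they are ceilings on the number missed.

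**The case against.** **The 45-day rule is an analysis convention, not a safety-collection rule.** It sits under missing data in SAP 6.2. Its Phase 2 precedent was an ADAS-cog analysis, and SAP 5.1.1 uses the on-treatment idea for the efficacy endpoint. The TEAE definition does not cite it. This stands: the plan does not define its safety period as 45 days and then fail to collect it. But the stated reason for the window, the long half-life, applies equally to safety, and the documents never say where treatment emergence ends. The boundary remains unreconciled.

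**A reader might infer that SAEs after Month 24 are captured solely when the investigator suspects the drug.** The documents do not support that. Unknown causality, malignancies, congenital anomalies and already ongoing events all have routes. None of these covers a new SAE judged not related.

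**A reader might also infer that SAE and death rates are understated by 6% or 20%.** They cannot be read that way. Protocol 9.3 and SAP 4.2.1 plan proportions of subjects, with no exposure-adjusted rate. The percentages are shares of time, not bias in a planned statistic.

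**The wording of Protocol 8.2 could mean the last visit of the last subject.** That would keep unconditional reporting open past most subjects' own final visit. It is the less natural reading, because Protocol 9.8 uses different words for that milestone, but the ambiguity is a further reason to state the end date plainly.

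**Where SAE collection ends is partly a design choice,** given that suspected-related events stay reportable without limit. That is fair as to the length of follow-up. It does not answer the missing end point for early terminators or the selective entry into the TEAE tables.

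**Conclusion.** The gap is real but narrow. New SAEs judged not related, other than malignancies and congenital anomalies, have no routine reporting route in a window that the SAP itself calls on-treatment, and Protocol 8.2 states no end of reporting for Early Termination subjects. Late SAEs therefore enter the primary safety summaries selectively by open-label attribution.

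The window is about 6% of on-treatment time for a 24-month completer, and it falls at the end of exposure with drug still present. For a subject stopping at 6 months the maximum is 20%, reached only if reporting stops on the day of the last dose. The number of SAEs missed cannot be derived from the documents. The exposure figures rest on the mean half-life, first-order decline and scheduled visit days. The finding is worth correcting because correction is cheap; it does not show that the safety conclusions would change.

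**What to change.** **Protocol 8.2.** Define the SAE reporting period as informed consent through 45 days after the last dose, for completers and Early Termination subjects alike. Require sites to report any SAE they learn of in that period regardless of causality. Keep the existing rule for suspected-related SAEs after it.

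**SAP 4.2.1 and 6.2.** Apply the same 45-day cut-off to treatment-emergent SAEs and TEAEs, so that the reporting period, the TEAE definition and the on-treatment window agree.

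**Cost.** Wording in three places and a few more SAE reports; no added visit. Capture will still be incomplete without a scheduled contact, because the 60-day follow-up in Protocol 8.7 covers only AEs already ongoing and creates no contact with a subject who had none. The study report should say so.

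Since SAP 1.5 already records premature termination, changing collection may be possible for few or no subjects. In that case the SAP cut-off can still be stated, SAEs with onset after the last visit can be tabulated separately, and the report should disclose that their capture depended on causality.
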